## Section D: Purpose and Objectives

The purpose of this study is to implement a parent-led, stepped-care cognitive behavioral therapy to children with ASD and anxiety. Specifically, we will (1) examine the effectiveness of Stepped-Care CBT (SC-CBT; e.g., starting with Step One parent-led, therapist-assisted treatment and then either maintenance or Step Two therapist-directed CBT), (2) examine the potential predictors of response to Step One that could be used as baseline tailoring variables to match children to the best level of care (i.e., Step One or CBT), and (3) examine the economic value of using a cost-effectiveness approach of SC-CBT. We expect that through Stepped-Care CBT, children’s anxiety levels will lessen.

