**Section F: Design/Procedure****F1. Design**

Select one category that most adequately describes your research:

d) Questionnaire/survey/interview

Discuss the research design including but not limited to such issues as: probability of group assignment, potential for subject to be randomized to placebo group, use of control subjects, etc.

A total of 200 children (aged 4-14) with a diagnosis of ASD and co-occurring anxiety and their parent/legal guardian will participate and receive SC-CBT treatment. In addition, all participants will be asked to cooperate in assessments that will occur at baseline, mid-treatment, post-treatment, and 3-month follow-up.

Inclusion Criteria:

- 1) The child is between the ages of 4 to 14 upon enrollment with a) an established diagnosis of ASD made by a standardized assessment (e.g., Autism Diagnostic Observation Schedule-Second Edition; Childhood Autism Rating Scale-Second Edition); and/or b) a score of 65 and above on the Social Responsiveness Scale-Second Edition (SRS-2).
- 2) The child has clinically elevated symptoms of anxiety and/or OCD as indicated by a Clinical Severity Rating of  $\geq 4$  from the Anxiety Disorders Interview Schedule (ADIS), made on diagnoses endorsed on the Mini-International Neuropsychiatric Interview for Children and Adolescents (MINI-Kid) at baseline assessment, and the Pediatric Anxiety Rating Scale  $> 12$ .
- 3) Anxiety and/or OCD is the primary presenting problem and the independent evaluator (IE) determines that the child is appropriate for the intervention focus.
- 4) One parent/guardian is able and willing to participate (i.e., parent-led therapist assisted treatment, attend study assessments).
- 5) The child has a Full Scale and Verbal Comprehension IQ  $> 70$  as assessed on the Differential Ability Scales-Second Edition (DAS-II) or Wechsler Abbreviated Scale of Intelligence-Second Edition (WASI-II). This level of intellectual ability is frequently used to demarcate the boundary of "high functioning"  $\pm$  ASD, and we and others have adopted this in our CBT trials for children with ASD to achieve acceptable external validity.
- 6) Both parent and child are able to read and/or understand English

Exclusion Criteria:

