**STEP ONE.** All participants will start with Step One, which includes 4 parent-led, therapist-assisted sessions over a 12-week period. Parents will receive a parent-child workbook to use in session with the therapist, and at home. During each of these 4 sessions, the therapist will review with parents the necessary skills for conducting exposures and will provide guidance in the delivery of exposures. Exposures, a hallmark of CBT for anxiety are used to gradually and repeatedly confront feared stimuli. For example, exposure therapy for a child fearful of dogs may begin with looking at pictures of dogs and standing across the park from a dog on a leash, to eventually petting a dog. Outside of session, parents will lead therapy using the provided workbook, which consists of a step-by-step approach for parents written on a 6th-grade level. Brief phone contacts between parent and staff will also be provided for support, coaching, and motivation. After completing Step One, a brief assessment will occur (i.e., the mid-treatment). If the child meets treatment response status, then the parent and child end treatment and proceed to the Maintenance phase, where parents and children will be encouraged to continue using the workbook and tools that they learned in Step One. If the child does not meet treatment response (i.e., does not improve), then s/he will 'step up' to Step Two.

**STEP TWO.** For those children who do not respond to Step One, they will be 'stepped up' to Step Two, which consists of 10 therapist-led, parent-supported sessions, each lasting 60-120 minutes over the course of 12 weeks. During Step Two, therapists will lead exposure tasks and teach children response strategies. These strategies will focus on providing children with anxiety-coping skills. In addition, parents will be taught (in weekly sessions) to support children in learning and maintaining anxiety-coping skills, especially when outside of sessions. These skills are encouraged to be practiced at school, in the community, and in peer-group settings. After completing Step Two, participants will end treatment and the post-assessment will occur. For those participants in the maintenance phase (i.e., treatment responders at Step One), the post-assessment will occur approximately 12 weeks after the completion of the mid-treatment (for consistency with procedures in Step Two). All participants will then be re-assessed 3-months, after completion of the post-treatment.

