#### ASSESSMENTS

All participants will be asked to cooperate in assessments that will occur as described above. All assessments will be conducted with an independent evaluator (IE). The IE will be an experienced clinician, trained professional, or advanced graduate trainee (supervised by a clinician). The measures that will be administered will include both IE-rated and participant-rated scales (please see attachment in section S). To reduce burden for families, post-assessment and 3-month follow-up measures will be completed through a secure connection using video-conferencing software (Zoom). Zoom is a secure HIPAA-compliant video-conferencing software.

In addition to completing rating scales, participants will be asked to participate in several objective assessment tasks, examining physiological and motor characteristics. These tasks will be given at baseline and at post-treatment, and will measure the participants gait performance (e.g., gait speed) and balance (e.g., center of mass sway). Both gait performance and balance will be assessed on-site during the in-person visits through the use of wearable sensors. Sensors transmit data to a BCM encrypted laptop via Bluetooth function (wireless), and data are saved in the laptop automatically. The sensor data will not include identifiable information such as name and date of birth. We will use HIPAA compliant BCM Box for transmitting the collected data and for storage. Data collected for each participant will be coded to ensure confidentiality. Only study personnel will have access to subjects' records. Data may also be shared with study's co-investigators (on this IRB protocol) through BCM Box. However, data that could in any way identify subjects will not be made public or shared. All of the outcomes in these tasks will be measured using previously validated wearable sensors (more information attached in section S).

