### Section G: Sample Size/Data Analysis

#### G1. Sample Size

How many subjects (or specimens, or charts) will be used in this study?

Local: 200      Worldwide: 200

Please indicate why you chose the sample size proposed:

We will enroll a total of 200 participants, which achieves sufficient power for the primary and secondary aims. Although we expect slight attrition, the below-mentioned analyses allow for attrition without the loss of data. While MLM does not provide for specific power analyses, the suggested power rules range from 20 participants per group, per level. As such, to be conservative with our power estimates, we aim to enroll 200 participants to ensure we are sufficiently powered for our analyses, accounting conservatively for attrition (~7% at Step One; ~15% at Step Two).

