#### G2. Data Analysis

Provide a description of your plan for data analysis. State the types of comparisons you plan (e.g. comparison of means, comparison of proportions, regressions, analysis of variance). Which is the PRIMARY comparison/analysis? How will the analyses proposed relate to the primary purposes of your study?

Data analysis will involve Multilevel Modeling (MLM) because of the *nesting* nature of the variables. More specifically, because the measures are repeated, the measures are considered the first level of the hierarchy, the individual children are considered the second level, and the treatment groups are considered the third level. A major advantage of MLM is its ability to handle missing data. While more traditional analyses use listwise deletion if a single time point is missing, MLM uses parameter estimates to maximize the use of existing data. Furthermore, the present study will implement a regression discontinuity analysis, which is an application of mixed models within MLM. This will allow us to examine the impact of treatment, without the use of random assignment, as this method allows for the use of groups that are similar at baseline, but then are designated by a predetermined selection cut point.

After assessing responder status and determining which participants receive Step Two treatment and which participants move to the maintenance phase, binary logistic regression will be utilized in an attempt to determine if there are factors significantly predicting group membership. Possible predictors include variables such as age, anxiety severity, internalizing/externalizing problems, and parent characteristics.

Cost-effectiveness analysis examines the relative value of SC-CBT (relative to CBT). CEA is performed from a societal perspective, meaning the costs to the healthcare system and the patient/parents are included. Treatment costs include

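### Aim 2 tests predictors of Step One response only on the yes/no step assignment, which loses at least about 36% of the information if response is a cut of one roughly normal score

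*Combined protocol and SAP*

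**What the plan says.** Section D states the second aim as to "examine the potential predictors of response to Step One that could be used as baseline tailoring variables", so that children can be matched to a level of care.

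Section G2 gives one analysis for it, run once responder status has decided who goes to Step Two and who to maintenance: "binary logistic regression will be utilized in an attempt to determine if there are factors significantly predicting group membership". The candidates are left open: "Possible predictors include variables such as age, anxiety severity, internalizing/externalizing problems, and parent characteristics". Nothing in G2 relates these predictors to a graded outcome.

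On the data, Section F2 (Treatment, Step One) says: "After completing Step One, a brief assessment will occur (i.e., the mid-treatment". It names no measure for that visit. The Assessments part of F2 refers to "both IE-rated and participant-rated scales (please see attachment in section S", an attachment outside the available text. F1 names the Pediatric Anxiety Rating Scale as an entry criterion.

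Two statements in G2 bear on whether a graded mid-treatment score exists. The multilevel model is chosen "because the measures are repeated, the measures are considered the first level of the hierarchy". The regression discontinuity separates the groups by a cut-off fixed in advance.

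On size, G1 says: "We will enroll a total of 200 participants, which achieves sufficient power for the primary and secondary aims". The support it offers is a rule of thumb for multilevel models and attrition of about 7% at Step One and 15% at Step Two.

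**The concern.** If responder status is a graded score cut in two, a child just short of the cut counts the same as one who did not change, and a child just past it the same as one who is well. A predictor related to the amount of improvement is then tested on only part of what was measured.

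The purpose of Aim 2 is to detect variables that could guide tailoring. A test with low power tends to miss moderate predictors, and a null result is easily read as showing that no useful predictor exists. G1 claims enough power for the secondary aims but offers no calculation for the logistic model, so any such loss is neither recognised nor offset.

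The mid-treatment score precedes step assignment. Using it for Aim 2 therefore raises no difficulty from some children later receiving Step Two.

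**Working it through.** **1. The plan's own figure.** The only stated size is 200. The rule in G1 (from 20 per group, per level), with two groups and three levels, gives 20 × 2 × 3 = 120. Allowing for 7% attrition, 120 / 0.93 gives 130; allowing for both rates, 120 / (0.93 × 0.85) = 120 / 0.7905 gives 152. Counting four time points as levels gives 160 / 0.7905, or 203, but the text does not define levels that way. No significance level, effect size, response rate or target power is given for Aim 2, so the sufficiency of 200 for the logistic model cannot be reproduced.

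**2. Inputs.**
- From the documents: 200 enrolled and about 7% lost at Step One, so 200 × 0.93 = 186 children with a mid-treatment assessment.
- Assumed: response is a cut of one roughly normal score; Step One response rate p of 20% to 80%; predictor correlation r with that score; two-sided 5% test of one predictor, with no multiplicity adjustment.

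**3. Is there a graded score?** The regression discontinuity needs a graded assignment variable, measured when the step is decided, which is mid-treatment. The multilevel model needs the measures repeated over visits. Both point to a graded mid-treatment score. This is inference, because the text does not name the score.

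**4. Information lost by the cut.** The relative efficiency of the yes/no outcome is φ(z_p)² / [p(1 − p)], where φ is the standard normal density at the cut. The smallest correlation detectable with 80% power is tanh[(1.960 + 0.842) / √(N − 3)], with N the equivalent sample size.

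| Assumed response | φ(z_p) | Relative efficiency | Loss | Equivalent of 186 | Detectable r |
|---|---|---|---|---|---|
| 50% | 0.3989 | 0.1592 / 0.25 = 0.637 | 36% | 118 | 0.255 |
| 30% or 70% | 0.3477 | 0.1209 / 0.21 = 0.576 | 42% | 107 | 0.268 |
| 20% or 80% | 0.2800 | 0.0784 / 0.16 = 0.490 | 51% | 91 | 0.290 |

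On the graded score itself, N = 186 gives a detectable r of 0.204. The loss is smallest at 50% response and grows towards either extreme.

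**5. Power at r = 0.20.** Approximate power is Φ[atanh(r) × √(N − 3) − 1.960], with atanh(0.20) = 0.2027.
- Linear, N = 186: 0.2027 × 13.53 − 1.960 = 0.782, power 0.78.
- Logistic, 50% response: 0.2027 × 10.74 − 1.960 = 0.217, power 0.59.
- Logistic, 30%: 0.2027 × 10.20 − 1.960 = 0.108, power 0.54.
- Logistic, 20%: 0.2027 × 9.39 − 1.960 = −0.057, power 0.48.

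Simulations of the two regressions (1,500 to 2,000 runs per setting, n = 186) agree: 0.78 to 0.80 for the linear model, and for the logistic model 0.58 to 0.59 at 50% response, 0.53 to 0.55 at 30% and 0.49 at 20%. With a baseline covariate correlated 0.5 with the outcome in both models, power was 0.89 for the linear model against 0.66 (50%) and 0.59 (30%) for the logistic.

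**6. Other effect sizes, from simulation.**

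| r | Linear | Logistic |
|---|---|---|
| 0.10 | 0.28–0.29 | 0.19–0.20 |
| 0.25 | 0.93–0.95 | 0.78–0.79 at 50%; 0.73–0.75 at 30% |
| 0.30 | 0.99 | 0.89–0.90 |
| 0.35 | above 0.99 | 0.97–0.98 |

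**7. If response is a separate rating.** The formula in step 4 then no longer applies, and the comparison can go either way. Suppose a predictor acts only through the rating (r = 0.25, 50% response). Linear against logistic power is then 0.78 against 0.78 if rating and score correlate 0.8, 0.65 against 0.77 at 0.7, and 0.53 against 0.78 at 0.6. If it acts only through the anxiety score (r = 0.20, rating and score correlated 0.8), logistic power is 0.42 at 50% response and 0.39 at 30%, against about 0.79 for the linear model.

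**The case against.** The strongest reply is that the plan answers the question it asks. Section D asks about response to Step One in order to choose a level of care. That choice is yes/no, and the logistic model targets it directly; the mean mid-treatment score is a different estimand. This stands, and it is why the linear model should sit beside the logistic model and not replace it.

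A second reply is that the premises are not documented. The available text does not define response beyond improvement, does not name the cut-off variable, gives no response rate and does not list the mid-treatment measures. Some of this may be in the attachments. This also stands: the loss is conditional, and step 7 of the working shows that a separate rating could remove or reverse the advantage. It does not remove the point, because the plan's own regression discontinuity presupposes a graded assignment score.

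A third reply is that predictors strong enough to direct individual children would mostly be found anyway. At correlations of 0.30 and above this is largely right. The gap matters most around 0.20 to 0.25.

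A fourth is that baseline anxiety severity is itself a listed candidate. In a model adjusted for the baseline score, its coefficient mainly reflects stability of the scale. This stands and is dealt with in the fix.

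**Conclusion.** The point holds in conditional form. Aim 2 rests on a single yes/no analysis, while the plan implies that a graded mid-treatment score will be available. If response is a cut of one roughly normal score, the minimum loss is about 36%, and it exceeds half at 20% or 80% response. Power for a moderate predictor then falls from about 0.8 to about 0.5 to 0.6. The response rates, the correlations and the form of the responder rule are assumptions; only the 200 and the 7% come from the documents.

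A reader might infer that the plan simply discards 36% to 42% of its information. The documents do not support that: the range presumes 30% to 70% response and a single-score rule, neither of which is stated. A reader might also infer that the logistic model is the wrong analysis, or that useful tailoring variables are bound to be missed. The first conflicts with the stated aim, and the second with the power at stronger correlations.

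**What to change.** In G2, under Aim 2:

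- Keep the logistic model, to express each result as a probability of needing Step Two.
- Add a prespecified, co-reported linear model of the mid-treatment anxiety score (the score that decides the step, if it is continuous), adjusted for the baseline score, to test each candidate predictor.
- Name that score, and say whether responder status is a cut of it or a separate rating. This settles whether the loss calculated above applies.
- State that the baseline-severity coefficient in the linear model reflects prediction of the mid-treatment score and not response, and that this predictor is read from the logistic model.

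The cost is one more model. No new data are needed if the score is collected as the plan implies. The downside is that the linear effects are in scale points, which is why the logistic model is kept for translation.

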direct (e.g., cost of therapy session), indirect (e.g., travel costs, missed work), and opportunity costs (e.g., value of lost time; see above for cost measures). CEA often incorrectly omits the opportunity cost of patient/parent time spent on therapy, phone support, and at-home parent-child meetings. Non-study, mental-health service costs include inpatient, outpatient, and school-based services and will be priced using the Texas Medicaid fee schedules. Research-specific costs (e.g., screening, research consent) for patients and staff are excluded. Incremental cost-effectiveness ratios (ICER) are computed as incremental costs divided by incremental changes in morbidity/outcomes (symptom reduction and change in impairment/functioning). If outcomes differ significantly, a non-parametric bootstrap with replacement method is used to generate a joint distribution of differential costs and outcomes. If outcomes do not differ, cost-effectiveness is determined by examining treatment costs. Mean and median ICER ratios are reported, as well as 95% confidence intervals. Cost-effectiveness acceptability curves examine the probability of falling below a variety of cost-effectiveness thresholds. In addition to the ICER approach, the net-benefit approach will be used to determine if findings are sensitive to method.

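### The cost-effectiveness analysis compares SC-CBT with CBT, but none of the 200 children forms a CBT comparator and no outside source of CBT data is named

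*Combined protocol and SAP*

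**What the plan says.** Section D lists the economic value of SC-CBT as the third of three aims. Section G2 names the comparator: "Cost-effectiveness analysis examines the relative value of SC-CBT (relative to CBT". It sets the viewpoint, "CEA is performed from a societal perspective", so family costs count as well as those of the healthcare system.

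The main measure follows: "Incremental cost-effectiveness ratios (ICER) are computed as incremental costs divided by incremental changes in morbidity/outcomes (symptom reduction and change in impairment/functioning". What comes next depends on the outcome comparison. When the difference is significant, resampling by non-parametric bootstrap "is used to generate a joint distribution of differential costs and outcomes". The other branch of the rule reads: "If outcomes do not differ, cost-effectiveness is determined by examining treatment costs". Acceptability curves are also planned, with net benefit as a check on whether the findings depend on the method.

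On design, Section F1 says that the 200 children and a parent or "guardian will participate and receive SC-CBT treatment". Section F2 confirms that every participant gets SC-CBT and starts with Step One (4 sessions over 12 weeks). Only Step One non-responders go on to Step Two (10 therapist-led sessions over 12 weeks). Section G2 says there is no random assignment.

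**The concern.** An incremental analysis needs two strategies, and this trial delivers one. G2 does not claim that the CBT side comes from the trial, but the available text gives no other origin for it.

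The wording also leaves room for a wrong substitute. Section D uses CBT in two senses: for Step Two inside the stepped-care package, and for the more intensive level of care to which a child might be matched instead of Step One. An analyst could therefore take the Step Two children as the CBT group.

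At stake is the conclusion on economic value. If the CBT benchmark is picked after SC-CBT costs are known, the choice can drive the answer.

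**Working it through.** **1. Size of the in-trial comparator.** Inputs: 200 enrolled, the same number locally and worldwide, so no other site adds an arm (G1); all 200 on SC-CBT (F1, F2).

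200 − 200 = 0 children on CBT alone.

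**2. What each planned output needs.**

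| Planned output (G2) | CBT data required |
|---|---|
| Incremental cost-effectiveness ratio | Mean costs and mean outcomes |
| Rule on whether outcomes differ | Outcomes and their variability |
| Bootstrap of differential costs and outcomes | Child-level costs and outcomes, since this bootstrap resamples individuals |
| Fallback on treatment costs | Costs |
| Acceptability curves | Joint distribution of the two differences |
| Net benefit, as a check on the ratio | Costs and outcomes |

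Both branches of the decision rule need CBT data, so the cost-only fallback does not avoid the gap. With 0 comparator children, none of these contrasts has an estimate from the trial.

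**3. Could Step Two children stand in?** G1 gives about 7% attrition at Step One and 15% at Step Two. After Step One, 200 × 0.93 = 186 remain. The Step One response rate p is not stated, so I assume 30% to 70%, and that drop-out is unrelated to response.

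- Entering Step Two: 186 × (1 − p) = 130 at p = 30%, 56 at p = 70%.
- Completing it: multiplied by 0.85, 111 and 47.

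Numbers are therefore not the obstacle. Every one of these children failed to respond to Step One and already carries its costs. Comparing them with the rest, or with SC-CBT as a whole, sets part of a strategy against the strategy that contains it.

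**4. Is a source named elsewhere?** Section C describes existing full CBT packages of 12 to 16 clinic sessions, as background and without costs or outcomes. Section F1 mentions earlier CBT trials only to support the IQ cut-off. Neither is tied to the economic analysis. G2 refers the reader to earlier text ("see above for cost measures") that is not in the available document, and the Assessments text in F2 says of the measures, "please see attachment in section S". A source could be in that attachment.

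**5. How much the benchmark matters (illustration only).** These are planned session counts, not costs, with p assumed and no drop-out. Sessions per child under SC-CBT = 4 + 10 × (1 − p).

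| Assumed p | SC-CBT sessions | Saving against 12 | Saving against 16 |
|---|---|---|---|
| 30% | 11 | 1 (8%) | 5 (31%) |
| 50% | 9 | 3 (25%) | 7 (44%) |
| 70% | 7 | 5 (42%) | 9 (56%) |

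The package chosen moves the saving by 16 − 12 = 4 sessions per child at every p. Session length, phone contacts and parent time are left out.

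**The case against.** The strongest reply is that G2 never promises a within-trial comparator. An external or modelled comparator is an ordinary way to obtain an incremental ratio, so the fault may be no more than an unnamed input. The document is a form whose details were partly moved to attachments, and the source may be there. This stands to the extent that the source's absence can be asserted only for the available text.

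Naming a source would not be enough to make the plan workable as written. The bootstrap needs child-level CBT data, and the societal perspective needs travel, missed work, parent time and other service use for those children. With published averages alone a model would be required, and G2 describes none.

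Three further points have some force:

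- The third aim in Section D does not mention CBT, so a descriptive report could satisfy it. This is correct, and it supports the remedy.
- Net benefit can be computed for one strategy. It then says nothing about CBT, and G2 plans it as a check on the incremental result.
- The planned regression discontinuity could compare the costs and outcomes of Step Two and maintenance near the response cut point. That contrast lies within SC-CBT and answers a different question.

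The session illustration also deserves limited weight. Its constant spread is simply the width of the 12 to 16 range, and sessions are not costs. The conclusion does not depend on it.

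**Conclusion.** The concern holds. The planned SC-CBT versus CBT analysis cannot be carried out on trial data, because the comparator is 0 of 200. That count rests only on the stated design. The statement that no external source is named applies to the available text.

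The effect is confined to the third aim: the effectiveness and predictor aims do not depend on it, and SC-CBT's own costs and outcomes can still be estimated. The plan should be corrected before the economic analysis begins.

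**What to change.** In the cost-effectiveness text of G2, take one of two routes.

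1. **Descriptive report.** Replace the ratio, bootstrap of differences, acceptability curves and net benefit with the mean societal cost per child under SC-CBT. Report it beside the outcomes already planned (symptom reduction and change in impairment or functioning), each with a bootstrap 95% confidence interval.
2. **External comparison.** Before analysis, name the source of CBT costs and outcomes, or cite the Section S attachment if it is there. Put its costs on the same societal perspective and give the time horizon and the handling of population differences. Label the comparison non-randomised and model-based, run a sensitivity analysis over the CBT inputs, and limit the conclusion to match.

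Under either route, state that Step Two children will not serve as the CBT comparator, and give CBT one meaning in Section D and G2.

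The change is a rewording, with no extra children or visits. The trial gives up a direct within-trial claim of cost-effectiveness against CBT, and the second route adds modelling work.

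### The cost-effectiveness rule lets cost alone decide after a non-significant outcome difference, with no margin, and does not say which planned analysis then governs

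*Combined protocol and SAP*

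**What the plan says.** Section D lists as the third aim to "examine the economic value of using a cost-effectiveness approach of SC-CBT". Section G2 (Data Analysis) sets the comparison as stepped-care CBT against CBT and defines the ICER as incremental cost over two kinds of outcome, one for symptoms and one for impairment or functioning.

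Two consecutive sentences then set the rule. The first makes the joint analysis conditional: "If outcomes differ significantly, a non-parametric bootstrap with replacement method is used to generate a joint distribution of differential costs and outcomes". The second covers the remaining case and hands the decision to cost, without a criterion of its own: "If outcomes do not differ, cost-effectiveness is determined by examining treatment costs".

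Three further planned analyses follow, none tied to either branch. The section promises interval estimates for the ratio: "Mean and median ICER ratios are reported, as well as 95% confidence intervals". It plans acceptability curves over a range of thresholds that it does not list. Finally, it adds a second method as a check on the first: "In addition to the ICER approach, the net-benefit approach will be used to determine if findings are sensitive to method".

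The documents give no margin, significance level or named test for the outcome comparison that selects the branch. Section G1 states: "We will enroll a total of 200 participants, which achieves sufficient power for the primary and secondary aims". It gives no effect size, SD or power figure for this contrast.

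**The concern.** A non-significant result says that the data are compatible with no difference. It does not say that a worthwhile difference has been ruled out. A rule that moves from non-significance to a comparison of costs sets the outcome difference to zero and discards its uncertainty. It does so more often when the data are less precise, which is when that uncertainty matters most.

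At stake is the Aim 3 conclusion. The cheaper option could be declared cost-effective although the data leave room for a loss of benefit that would outweigh the saving. The more effective option could equally be passed over because its advantage missed significance. Which option this would favour is not known. The effectiveness analysis for Aim 1 is not affected.

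**Working it through.** **1. Which branch applies.** The plan attaches no figure to this rule, so there is none to reproduce; the first check is on the text. The first sentence has a criterion: a significant difference. The second has none of its own. Its natural meaning is the complement of the first, that is, not significant. This is an inference, but no other criterion in the documents could replace it. The trigger is also incomplete: two kinds of outcome are named, and the plan does not say which test selects the branch or what follows if the two disagree.

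**2. What the cost-only branch removes.** Let ΔE be the outcome difference, ΔC the cost difference and λ the threshold value of one unit of outcome. Incremental net benefit is

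INB = λ·ΔE − ΔC, with var(INB) = λ²·var(ΔE) + var(ΔC) − 2λ·cov(ΔE, ΔC).

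Deciding on cost alone amounts to setting ΔE, var(ΔE) and the covariance to zero. A p-value above the significance level justifies none of these.

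**3. What the unconditional sentences leave open.** Acceptability curves and net benefit use cost and outcome jointly, and they are written without a condition. An acceptability curve needs a joint distribution, and the only source stated is the bootstrap, which is conditional. The verb of decision belongs to the cost-only sentence, while net benefit is described as a check on sensitivity to method. After a non-significant test the plan therefore holds a cost-only rule and a set of joint analyses, and does not rank them.

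**4. Illustration of size.** The inputs are assumptions: two groups of n each with patient-level data, SD 1, and a two-sided 0.05 test. For a true difference d, the chance of non-significance is close to Φ(t_crit − d·√(n/2)).

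- n = 100, d = 0.3: 0.3 × √50 = 2.121, and t_crit = 1.972 on 198 df. Φ(−0.149) ≈ 0.44; the noncentral t gives 0.440.
- Same, baseline-adjusted with r = 0.5: d/√(1 − r²) = 0.3/0.866 = 0.346, and 0.346 × √50 = 2.449. Φ(−0.477) ≈ 0.32; the noncentral t gives 0.316.

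Range over the assumed true difference, n = 100 per group (noncentral t):

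| True difference (SD) | Non-significant, unadjusted | Non-significant, r = 0.5 |
|---|---|---|
| 0.2 | 71% | 63% |
| 0.3 | 44% | 32% |
| 0.4 | 20% | 10% |
| 0.5 | 6% | 2% |

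Range over the assumed group size, d = 0.3, unadjusted:

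- n = 79 (both attrition rates in Section G1 applied to everyone: 200 × 0.93 × 0.85 = 158, halved): 0.3 × √39.5 = 1.885. With a critical value of 1.96, Φ(0.075) ≈ 53%.
- n = 200 per group: 0.3 × √100 = 3.0. Φ(1.966 − 3.0) ≈ 15%.

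With n = 100, an observed difference of exactly zero still has an unadjusted 95% interval of ±1.972 × √(2/100) = ±0.28 SD.

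**The case against.** The strongest reply is that the joint analysis is not abandoned. ICER intervals, acceptability curves and net benefit are planned in the same section without any condition. This stands. A reader might infer that the plan makes no provision for joint analysis after a non-significant result, and the text does not support that: only the bootstrap is expressly conditional. What remains is that the plan neither ranks these analyses against the cost-only rule nor says what would generate the curves if the bootstrap is not run.

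A second reply is that the sentence speaks of outcomes that do not differ, without mentioning significance. That is also true, so the equation with non-significance is an inference. If a stricter meaning was intended, however, it needs a margin, and none is given.

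A third reply is that the figures do not describe this trial. That is correct. Section F2 (Treatment) gives every participant stepped-care CBT, so a 100/100 split against CBT cannot arise from the documented design. If an external patient-level CBT group were used, the groups could be larger and the miss rate lower. If CBT values came from a model or published figures, these rates would not apply.

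**Conclusion.** The point holds as a defect in the decision rule for Aim 3. On its natural reading, the rule takes a non-significant outcome difference as no difference, lets cost decide, and has no margin behind it. Because joint analyses are also planned without a condition, the plan is unclear about which result governs.

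The size is illustrative. At an assumed 100 per group, a true difference of 0.3 SD would be non-significant about 44% of the time, or about 32% with baseline adjustment at r = 0.5. This rests on assumed group sizes, effect, correlation and significance level.

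A reader might take 44% as this trial's error rate, or infer that 200 participants are too few for any usable margin. The documents support neither, since they define no CBT group, no allocation and no margin.

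The source of the CBT comparator is a separate and prior question. Settling it would not cure this rule. The matter should be corrected before analysis.

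**What to change.** In Section G2:

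1. Delete the condition on significance. Run the bootstrap, 95% intervals, acceptability curves and net benefit whatever the outcome test shows, for both symptom reduction and impairment or functioning. The question of which outcome test opens the gate then falls away.
2. State that the Aim 3 conclusion rests on these joint analyses.
3. Allow a cost-only conclusion only if an equivalence or non-inferiority margin, set and justified in advance, is met.

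Define the source of the CBT outcomes and costs first, as a separate matter, since no joint or cost-only comparison can be run without it.

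The cost is a change of wording. The methods are already planned and need no data beyond what Aim 3 already requires. The drawback is a slightly less simple result than a single cost comparison, and a margin must be justified if a cost-only conclusion is wanted.
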